5.7 Outcomes Research Assessments

Quality of Life (QOL) instruments will be given to all English speaking subjects who have been previously taking an anticoagulant at the Day 1 visit. These include patient/proxy reported outcome or quality of life (e.g, pediatric quality of life inventory [PedsQL]) generic core and cardiac modules, and Kids Informed Decrease Complications Learning on Thrombosis [KIDCLOT®]). Subjects who are newly prescribed an anticoagulant at study entry will be given the PedsQL at the Day 1 visit, but because some exposure to anticoagulation therapy is necessary to complete the KIDCLOT, they will be given the KIDCLOT at the Week 2 visit. The QOL instruments need to be completed at the time of the visit.

Additionally, the QOL instruments will be administered at the Month 6 visit, the end of study treatment (for subjects who discontinue study drug early) or Month 12 visit.

5.8 Other Assessments

Not applicable.

6 ADVERSE EVENTS

An *Adverse Event (AE)* is defined as any new untoward medical occurrence or worsening of a preexisting medical condition in a clinical investigation subject administered study drug and that does not necessarily have a causal relationship with this treatment. An AE can therefore be any unfavorable and unintended sign (such as an abnormal laboratory finding), symptom, or disease temporally associated with the use of study drug, whether or not considered related to the study drug.

The causal relationship to study drug is determined by a physician and should be used to assess all AE. The causal relationship can be one of the following:

Related: There is a reasonable causal relationship between study drug administration and the AE.

Not related: There is not a reasonable causal relationship between study drug administration and the AE.

The term "reasonable causal relationship" means there is evidence to suggest a causal relationship.

AEs can be spontaneously reported or elicited during open-ended questioning, examination, or evaluation of a subject. (In order to prevent reporting bias, subjects should not be questioned regarding the specific occurrence of one or more AEs.)

BMS will be reporting AEs to regulatory authorities and ethics committees according to local applicable laws including European Directive 2001/20/EC and FDA Code of Federal Regulations 21 CFR Parts 312 and 320.

6.1 Serious Adverse Events

A *Serious Adverse Event (SAE)* is any untoward medical occurrence that at any dose:

- results in death
- is life-threatening (defined as an event in which the subject was at risk of death at the time of the event; it does not refer to an event which hypothetically might have caused death if it were more severe)
- requires inpatient hospitalization or causes prolongation of existing hospitalization (see **NOTE** below)
- results in persistent or significant disability/incapacity
- results in a congenital anomaly/birth defect
- is an important medical event (defined as a medical event(s) that may not be immediately life-threatening or result in death or hospitalization but, based upon appropriate medical and scientific judgment, may jeopardize the subject or may require intervention [e.g., medical, surgical] to prevent one of the other serious outcomes listed in the definition above.) Examples of such events include, but are not limited to, intensive treatment in an emergency room or at home for allergic bronchospasm; blood dyscrasias or convulsions that do not result in hospitalization.). Potential drug induced liver injury (DILI) is also considered an important medical event. (See [Section 6.6](#) for the definition of potential DILI.)
- Suspected transmission of an infectious agent (e.g., pathogenic or nonpathogenic) via the study drug is an SAE
- Although pregnancy, overdose, cancer, and potential DILI are not always serious by regulatory definition, these events must be handled as SAEs. (See [Section 6.1.1](#) for reporting of pregnancies)
- Any component of a study endpoint that is considered related to study therapy (e.g., death is an endpoint, if death occurred due to anaphylaxis, anaphylaxis must be reported) should be reported as SAE (see [Section 6.1.1](#) for reporting details)

NOTE:

The following hospitalizations are not considered SAEs in BMS clinical studies:

- a visit to the emergency room or other hospital department lasting < 24 hours, that does not result in admission (unless considered an important medical or life-threatening event)

- elective surgery, planned prior to signing consent
- admissions as per protocol for a planned medical/surgical procedure
- routine health assessment requiring admission for baseline/trending of health status (e.g., routine colonoscopy)
- medical/surgical admission other than to remedy ill health and planned prior to entry into the study. Appropriate documentation is required in these cases
- admission encountered for another life circumstance that carries no bearing on health status and requires no medical/surgical intervention (e.g., lack of housing, economic inadequacy, caregiver respite, family circumstances, or other administrative reason)
- Admission for administration of anticancer therapy in the absence of any other SAEs

6.1.1 Serious Adverse Event Collection and Reporting

Sections 5.6.1 and 5.6.2 in the Investigator Brochure (IB) and the local product label for apixaban represent the Reference Safety Information to determine expectedness of SAEs for expedited reporting. For active comparators VKA and LMWH, the local product label (e.g., USPI, SmPC, etc.) will be used as Reference Safety Information to determine expectedness of SAEs for expedited reporting. Following the subject's written consent to participate in the study, all SAEs, whether related or not related to study drug, must be collected, including those thought to be associated with protocol-specified procedures. All SAEs that occur during the screening period and within 30 days of discontinuation of dosing must be collected.

The investigator must report any SAE that occurs after these time periods and that is believed to be related to study drug or protocol-specified procedure.

An SAE report must be completed for any event where doubt exists regarding its seriousness.

If the investigator believes that an SAE is not related to study drug, but is potentially related to the conditions of the study (such as withdrawal of previous therapy or a complication of a study procedure), the relationship must be specified in the narrative section of the SAE Report Form.

SAEs, whether related or not related to study drug, and pregnancies must be reported to BMS (or designee) within 24 hours of awareness of the event. SAEs must be recorded on the SAE Report Form; pregnancies on a Pregnancy Surveillance Form (electronic or paper forms). The preferred method for SAE data reporting collection is through the electronic CRF. The paper SAE/pregnancy surveillance forms are only intended as a back-up option when the electronic CRF system is not functioning. In this case, the paper forms are to be transmitted via email or confirmed facsimile transmission to:

SAE Email Address: Refer to Contact Information list.

SAE Facsimile Number: Refer to Contact Information list.

For studies capturing SAEs through electronic data capture (EDC), electronic submission is the required method for reporting. In the event the electronic system is unavailable for transmission,

paper forms must be used and submitted immediately. When paper forms are used, the original paper forms are to remain on site.

SAE Telephone Contact (required for SAE and pregnancy reporting): Refer to Contact Information list.

If only limited information is initially available, follow-up reports are required. (Note: Follow-up SAE reports must include the same investigator term(s) initially reported.)

If an ongoing SAE changes in its intensity or relationship to study drug or if new information becomes available, the SAE report must be updated and submitted within 24 hours to BMS (or designee) using the same procedure used for transmitting the initial SAE report.

All SAEs must be followed to resolution or stabilization.

6.2 Nonserious Adverse Events

A *nonserious AE* is an AE not classified as serious.

6.2.1 Nonserious Adverse Event Collection and Reporting

The collection of nonserious AE information should begin at initiation of study drug.

Nonserious AEs should be followed to resolution or stabilization, or reported as SAEs if they become serious (see [Section 6.1.1](#)). Follow-up is also required for nonserious AEs that cause interruption or discontinuation of study drug and for those present at the end of study treatment as appropriate. All identified nonserious AEs must be recorded and described on the nonserious AE page of the CRF (paper or electronic).

Completion of supplemental CRFs may be requested for AEs and/or laboratory abnormalities that are reported/identified during the course of the study.

6.3 Laboratory Test Result Abnormalities

The following laboratory test result abnormalities should be captured on the nonserious AE CRF page or SAE Report Form (electronic) as appropriate. Paper forms are only intended as a back-up option when the electronic system is not functioning.

- Any laboratory test result that is clinically significant or meets the definition of an SAE
- Any laboratory test result abnormality that required the subject to have study drug discontinued or interrupted
- Any laboratory test result abnormality that required the subject to receive specific corrective therapy

It is expected that wherever possible, the clinical rather than laboratory term would be used by the reporting investigator (e.g., anemia versus low hemoglobin value).

6.4 Pregnancy

If, following initiation of the study drug, it is subsequently discovered that a study subject is pregnant or may have been pregnant at the time of study exposure, including during at least

5 half-lives after product administration, the investigator must immediately notify the BMS Medical Monitor/designee of this event and complete and forward a Pregnancy Surveillance Form to BMS Designee within 24 hours of awareness of the event and in accordance with SAE reporting procedures described in [Section 6.1.1](#).

In most cases, the study drug will be permanently discontinued in an appropriate manner (e.g., dose tapering if necessary for subject safety). Please call the BMS Medical Monitor within 24 hours of awareness of the pregnancy.

Follow-up information regarding the course of the pregnancy, including perinatal and neonatal outcome and, where applicable, offspring information must be reported on the Pregnancy Surveillance Form.

Any pregnancy that occurs in a female partner of a male study participant should be reported to BMS. Information on this pregnancy will be collected on the Pregnancy Surveillance Form.

6.5 Overdose

An overdose is defined as the accidental or intentional administration of any dose of a product that is considered both excessive and medically important. All occurrences of overdose, if excessive and medically important, must be reported as an SAE (see Section 6.1.1 for reporting details).

6.6 Potential Drug Induced Liver Injury (DILI)

The following guidelines are intended to identify and manage subjects with liver function abnormalities. Specific laboratory test criteria and instructions for further follow up are provided.

If at any time during the treatment period a subject's liver function test (LFT) results show:

- An isolated elevation of either ALT/AST ≥ 5 x ULN AND/OR a direct (conjugated) bilirubin > 2 x ULN, obtain the following laboratories: ALT, AST, total bilirubin, direct bilirubin, alkaline phosphatase, GGT, CK as soon as possible (i.e. within 3 days)
- If the repeat tests indicate:
 - ALT/AST < 5 x ULN and conjugated bilirubin ≤ 2 x ULN, study medication may continue
 - ALT/AST ≥ 5 x ULN AND/OR the conjugated bilirubin is > 2 x ULN, the study medication must be interrupted

The study medication must be interrupted if:

- Clinical jaundice is present in a subject at any time unless there is an alternative causative factor such as Gilbert or Dubin-Johnson syndrome

OR

- If ALT/AST ≥ 5 x ULN on any two consecutive occasions

OR

- Conjugated bilirubin > 2 x ULN on any two consecutive occasions

All subjects with an ALT/AST $\geq 5 \times$ ULN or direct bilirubin $> 2 \times$ ULN will be followed weekly until ALT/AST returns to $< 3 \times$ ULN or to baseline, and the conjugated bilirubin returns to $\leq 1.5 \times$ ULN or to baseline.

If study medication is discontinued due to elevated ALT, AST, OR bilirubin, as defined above, inform the medical Monitor and perform the following:

- aPTT, fibrinogen to assess liver synthetic function
- Abdominal ultrasound, including liver and hepatobiliary system
- Hepatitis screen (anti-HAV, HBsAg, anti-HBc, anti-HBs and anti-HCV)
- Obtain relevant specialist consultation

6.7 Other Safety Considerations

Any significant worsening noted during interim or final physical examinations, any other potential safety assessment required or not required by protocol should also be recorded as a nonserious or serious AE, as appropriate, and reported accordingly.

7 DATA AND SAFETY MONITORING BOARD AND OTHER EXTERNAL COMMITTEES

7.1 Data and Safety Monitoring Board

This study will be conducted under the monitoring of an independent Data Safety Monitoring Board (DSMB), whose activities will be described in a DSMB charter. In addition, the DSMB will use their clinical and statistical judgment to recommend that the study proceed or be terminated early.

7.2 Steering Committee

An academic Steering Committee, participated in the development of the protocol, and will provide ongoing scientific and operational oversight to the study. The Steering Committee will monitor all aspects of the study, make recommendations to the sponsor and the Pediatric Heart Network (PHN) based on the DSMB recommendations, and oversee the presentation of the trial results and any publications.

7.3 Event Adjudication Committee

The EAC, as described in the EAC charter, is an independent committee constituted by experienced clinicians independent of the Investigators and the Sponsor. The responsibilities of the EAC are to validate all study endpoints that are central to the accuracy of results and conclusions of the trial. Specifically, the EAC will classify endpoints according to documentation provided by Investigators. Adjudicated results will be the basis for the final primary analyses.

8 STATISTICAL CONSIDERATIONS

8.1 Sample Size Determination

Due to anticipated low rates of thromboembolic⁶ and bleeding^{5,6} events in the study population and other numerous barriers,³⁸ a Phase 3 trial requiring an excessively large sample size is impracticable. However, there remains a need to understand the safety and PK/PD profile of apixaban in children with heart disease and gather preliminary data on efficacy that could be used to develop future studies. Therefore, the study is designed to obtain apixaban PK, PD, safety information, and exploratory efficacy data, and is a descriptive study for which the safety, PK/PD, and efficacy variables will be summarized. The study will still include a randomized comparison group with standard anticoagulants as a frame of reference regarding frequencies of bleeding and thromboembolic events in the pediatric setting. This approach has been recommended by the Subcommittee on Pediatric and Neonatal Hemostasis and Thrombosis of the International Society on Thrombosis and Haemostasis (ISTH).³⁹

With a treatment period up to 12 months, the sample size of approximately 200 subjects (approximately 133 in the apixaban group and approximately 67 in the SOC group) is a feasible sample size that will provide a robust PK/PD database, and reasonable safety data along with limited efficacy data in pediatric subjects with heart disease who need chronic thromboprophylaxis. More specifically, approximately 533 blood samples will be obtained during the study to characterize apixaban PK and PD in approximately 133 apixaban treated subjects aged 28 days to < 18 years. The data collected in the current study will be combined with available data from two other pediatric PK studies for population PK/PD analyses, providing the ability to fully capture the pharmacokinetic disposition in this special patient population. In addition, these analysis will provide robust data to inform apixaban dosing in the pediatric cardiac population across a broad age spectrum. The observed AE, bleeding events, QOL and efficacy data from this study will provide insight into the expected event rates for the pediatric population treated with apixaban or SOC to inform benefit-risk.

The following examples of potential results, with anticipated precision around the estimate, may provide an understanding of the data that the study will generate, and may offer insight into how the trial data may be interpreted.

Possible Safety Outcome

The primary safety endpoint (a composite of adjudicated major or clinically relevant non-major bleeding) event rate is not well characterized in children. Based on two randomized studies in pediatric patients with congenital heart disease,^{6,5} one randomized study in pediatric patients with VTE events⁴⁰, and adult data in the stroke prevention trial ARISTOTLE¹⁷, event rates of 2 to 12% may be expected. Based on this event rate range, the following may be a safety outcome of this trial:

Table 8.1-1: Number of Safety Events, Event Rate, and 95% Confidence Intervals for the Primary Safety Outcome in the Apixaban Group (N=133)

| # of Events | Event Rate | 95% CI (%) |
|-------------|------------|-------------|
| 2 | 1.5% | 0.2 to 5.3 |
| 3 | 2.3% | 0.5 to 6.4 |
| 4 | 3% | 0.8 to 7.5 |
| 7 | 5.3% | 2.1 to 10.5 |
| 9 | 6.8% | 3.1 to 12.5 |
| 16 | 12% | 7.0 to 18.8 |

Note: The primary safety outcome will be the incidence of adjudicated major or clinically relevant non-major bleeding. Each type of adjudicated bleeding will be summarized using counts and frequencies in each treatment arm.

Table 8.1-2: Number of Safety Events, Event Rate, and 95% Confidence Intervals for the Primary Safety Outcome in the Comparator Group (N=67)

| # of Events | Event Rate | 95% CI (%) |
|-------------|------------|-------------|
| 1 | 1.5% | 0 to 8.0 |
| 2 | 3% | 0.4 to 10.4 |
| 4 | 6% | 1.7 to 14.6 |
| 5 | 7.5% | 2.5 to 16.6 |
| 6 | 9% | 3.4 to 18.5 |
| 8 | 11.9% | 5.3 to 22.2 |

Note: The primary safety outcome will be the incidence of adjudicated major or clinically relevant non-major bleeding. Each type of adjudicated bleeding will be summarized using counts and frequencies in each treatment arm.

To further provide an understanding of the data that the study will generate, examples of potential differences in bleeding event rates and anticipated precision around the estimate between apixaban and comparator are shown in [Table 8.1-3](#). Since the relative safety profile of apixaban in pediatric patients with cardiac disease is unknown, both scenarios of better safety and worse safety of apixaban relative to comparator are displayed.

Table 8.1-3: Difference in Event Rates and 95% Confidence Intervals between Comparator Group and Apixaban Group

| Event Rate for Comparator (N=67) | Event Rate for Apixaban (N=133) | Difference of Event Rates (Comparator-Apixaban) | 95% CI (%) of Difference of Rates |
|----------------------------------|---------------------------------|---|-----------------------------------|
| 3% | 2.3% | 0.7% | -4.0 to 8.1 |
| | 6% | -3% | -8.9 to 4.8 |
| | 9.8% | -6.8% | -13.4 to 1.5 |
| 10.5% | 2.3% | 8.2% | 1.5 to 17.9 |
| | 6% | 4.5% | -3 to 14.5 |
| | 9.8% | 0.7% | -7.5 to 11.1 |
| | 15% | -4.5% | -13.4 to 6.3 |
| | 22.6% | -12.1% | -21.6 to -0.7 |

CI - confidence interval

Potential Power to Detect Possible Differences between Apixaban and Comparator in Safety Endpoints

As discussed above, this study is intended to provide safety and PK data for at least 133 patients exposed to apixaban, and is not expected to be fully powered for either efficacy or safety due to the low incidence of thromboembolic and bleeding events in children. For completeness, however, a range of power for the primary safety endpoint is provided in [Table 8.1-4](#) and [Table 8.1-5](#). This estimation is based on a sample size of approximately 200 subjects and an event rate range of 2-12%, using Fisher’s exact test and a 2-sided 0.05 significance level. Both scenarios of better safety and worse safety of apixaban relative to comparator are displayed.

Table 8.1-4: Possible Power to Detect a Significant Difference between Comparator Group and Apixaban Group for the Primary Safety Endpoint (Assuming Apixaban is Better)

| Comparator | | | Apixaban | | | Power to Detect a Significant Difference |
|-------------|------------|---------------------------|-------------|------------|---------------------------|--|
| Sample Size | Event Rate | Expected Number of Events | Sample Size | Event Rate | Expected Number of Events | |
| 67 | 11.9% | 8 | 133 | 2.3% | 3 | 75% |
| | 13.4% | 9 | | 2.3% | 3 | 83% |
| | 11.9% | 8 | | 3.8% | 5 | 65% |
| | 16.4% | 11 | | 3.8% | 5 | 82% |
| | 11.9% | 8 | | 6% | 8 | 27% |
| | 23.9% | 16 | | 8.3% | 11 | 81% |

Note: The primary safety endpoint will be a composite of adjudicated major or clinically relevant non-major bleeding. Power is calculated using Fisher’s exact test and a two-sided alpha=0.05.

Table 8.1-5: Possible Power to Detect a Significant Difference between Comparator Group and Apixaban Group for the Primary Safety Endpoint (Assuming Apixaban is Worse)

| Comparator | | | Apixaban | | | Power to Detect a Significant Difference |
|-------------|------------|---------------------------|-------------|------------|---------------------------|--|
| Sample Size | Event Rate | Expected Number of Events | Sample Size | Event Rate | Expected Number of Events | |
| 67 | 3% | 2 | 133 | 11.3% | 15 | 47% |
| | 3% | 2 | | 15.8% | 21 | 84% |
| | 4.5% | 3 | | 11.3% | 15 | 28% |
| | 4.5% | 3 | | 18.8% | 25 | 82% |
| | 6% | 4 | | 11.3% | 15 | 35% |
| | 6% | 4 | | 21.1% | 28 | 81% |
| | 9% | 6 | | 15.8% | 21 | 30% |
| | 9% | 6 | | 25.5% | 34 | 80% |

Note: The primary safety endpoint will be a composite of adjudicated major or clinically relevant non-major bleeding. Power is calculated using Fisher’s exact test and a two-sided alpha=0.05.

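### Three powers in Tables 8.1-4 and 8.1-5 are about 9 to 19 points too high for their printed inputs (a fourth is 3 points high), and the stated 2-12% basis does not match the tables

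*Combined protocol and SAP*

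**What the plan says.** Section 8.1 (Sample Size Determination) sets the sample at about 200, with "approximately 133 in the apixaban group and approximately 67 in the SOC group". Under Possible Safety Outcome it says of the primary composite of major or clinically relevant non-major bleeding that "event rates of 2 to 12% may be expected".

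The power subsection says the study "is not expected to be fully powered for either efficacy or safety", and then: "For completeness, however, a range of power for the primary safety endpoint is provided in" Tables 8.1-4 and 8.1-5. Its basis is given as "This estimation is based on a sample size of approximately 200 subjects and an event rate range of 2-12"%. The note under each table repeats the method: "Power is calculated using Fisher’s exact test and a two-sided alpha=0.05".

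Table 8.1-4 covers apixaban better (six rows). Table 8.1-5, titled "Possible Power to Detect a Significant Difference between Comparator Group and Apixaban Group for the Primary Safety Endpoint (Assuming Apixaban is Worse"), has eight rows. Every row prints both event rates, both expected counts and a power.

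**The concern.** Because the test, alpha, arm sizes, rates and counts are all printed, each power can be recalculated without any assumption. Two things look wrong.

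First, Table 8.1-5 contradicts itself before any calculation. With apixaban fixed at 11.3%, moving the comparator from 4.5% to 6% narrows the difference from 6.8 to 5.3 points, yet the stated power rises from 28% to 35%. With the arm sizes fixed, at least one of those entries must be wrong.

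Second, the basis sentence names 2-12%, but the tables run up to 23.9% (comparator) and 25.5% (apixaban). A reader could take the 80% figures as power within the expected range of event rates.

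At stake is how readers judge what the trial could detect on its primary safety endpoint. Two of the three large discrepancies are in the table where apixaban is worse. In one of them the stated 35% is more than twice the chance of detecting a near doubling of bleeding (6% to 11.3%), so a non-significant result would look more reassuring than it should.

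**Working it through.** **Inputs, all from Section 8.1.** Comparator n = 67, apixaban n = 133; two-sided Fisher's exact test at 0.05; rates and counts as printed in each row.

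**Method.** Let X ~ Bin(67, p_C) and Y ~ Bin(133, p_A). Then

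power = Σ Pr(X = x) · Pr(Y = y), summed over all (x, y) whose two-sided Fisher p-value is ≤ 0.05,

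taken over all 68 × 134 possible outcomes. It was run with p = count/n and again with the printed rates.

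**Results, from the printed counts.**

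| Table | Comparator | Apixaban | Stated | Computed |
|---|---|---|---|---|
| 8.1-4 | 11.9% (8) | 2.3% (3) | 75 | 75.8 |
| 8.1-4 | 13.4% (9) | 2.3% (3) | 83 | 84.0 |
| 8.1-4 | 11.9% (8) | 3.8% (5) | **65** | **54.3** |
| 8.1-4 | 16.4% (11) | 3.8% (5) | 82 | 83.0 |
| 8.1-4 | 11.9% (8) | 6% (8) | 27 | 27.1 |
| 8.1-4 | 23.9% (16) | 8.3% (11) | 81 | 82.0 |
| 8.1-5 | 3% (2) | 11.3% (15) | 47 | 47.3 |
| 8.1-5 | 3% (2) | 15.8% (21) | **84** | **81.0** |
| 8.1-5 | 4.5% (3) | 11.3% (15) | 28 | 28.5 |
| 8.1-5 | 4.5% (3) | 18.8% (25) | 82 | 82.8 |
| 8.1-5 | 6% (4) | 11.3% (15) | **35** | **16.2** |
| 8.1-5 | 6% (4) | 21.1% (28) | 81 | 81.8 |
| 8.1-5 | 9% (6) | 15.8% (21) | **30** | **21.5** |
| 8.1-5 | 9% (6) | 25.5% (34) | 80 | 80.8 |

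Ten rows agree to within about 1 point, which confirms that this is the plan's method. The other four are too high by 10.7, 3.0, 18.8 and 8.5 points, in table order. From the printed rates instead of the counts they compute to 53.4, 80.9, 16.1 and 21.3.

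**Rounding.** Moving each printed rate by ±0.05 points gives 52.3-54.5, 80.1-81.7, 15.5-16.7 and 20.7-21.9. None of these ranges reaches the stated value.

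**A different test.** For the 65% row, the doubled one-sided Fisher p, mid-P, one-sided Fisher at 0.05 and the two-sided normal approximation give 45.8, 57.5, 58.3 and 58.7. For the 35% row they give 14.3, 21.5, 24.8 and 20.4. One-sided Fisher at 0.05 does give 30.3 for the 30% row, but it breaks rows that now match (59.2 against the stated 47).

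**The reversal.** At apixaban 11.3%, computed power falls from 28.5% (comparator 4.5%) to 16.2% (comparator 6%), as it should when the difference shrinks.

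**Which entry is faulty.** In each of the four rows the printed rate and count agree with each other (for example 8/67 = 11.9%, 5/133 = 3.8%, 15/133 = 11.3%, 21/133 = 15.8%). Nearby counts come close to the stated powers: 8 vs 4 gives 65.1, 2 vs 22 gives 84.8, 4 vs 19 gives 35.6 and 6 vs 23 gives 30.6. That is compatible with slips in the inputs, but it is not proof.

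**The range sentence.** Rows with a rate above 12%: three in Table 8.1-4 (13.4, 16.4, 23.9) and five in Table 8.1-5 (15.8 twice, 18.8, 21.1, 25.5), so 8 of 14. All seven rows with stated power of 80% or more are among them. In the six rows with both rates within 2-12%, the highest stated power is 75%. A grid over 2-12% in steps of 0.5 points has its maximum of 79.7% at comparator 12% vs apixaban 2%. With apixaban worse, the maximum is 69.2% (2% vs 12%).

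**The case against.** The best counter-argument concerns weight, not arithmetic. The study is descriptive, its size is justified by feasibility, and power is offered only for completeness. Section 8.4.3 plans event rates, differences, confidence intervals and a Mantel-Haenszel relative risk, with no hypothesis test, so no planned test has the power shown. No correction crosses 80%: three rows are underpowered before and after, and the fourth stays above 80%. All of this stands and limits the consequence. It does not make the printed values right, and Section 8.1 offers these examples as a guide to interpreting the data.

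On the range, the lower-rate arm lies inside 2-12% in every row. Raising the other rate until power reaches about 80% is a normal way to show a detectable difference, and each row prints its own rates. That reading is possible, but the sentence does not say it. As written, it describes the whole estimation as based on 2-12%.

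The nearby-count matches were found after the fact and are weak evidence of cause; each would need the printed rate and the printed count to be wrong together. That is fair, and no correction is rested on them.

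**Conclusion.** The point holds: these powers are wrong as written for their printed inputs. Three rows are overstated: 65% for about 54%, 35% for about 16% and 30% for about 21%. A fourth is slightly overstated, 84% for about 81%. The result needs nothing beyond the method, arm sizes, rates and counts that the plan prints, and the ten matching rows support the calculation. Whether the power or the rate and count is the faulty entry in each row cannot be told from the documents.

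The range sentence also does not describe the tables, since every row at 80% or more depends on a rate above 12%. This should be fixed, but its reach is limited to illustrative figures. The confidence intervals in Table 8.1-3 are not questioned here.

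**What to change.** Check the rates, counts and powers of the four rows against the source output. If the printed rates and counts stand, restate the powers as 54%, 16%, 21% and 81%. If they do not, correct the rates and counts and keep the powers that match them.

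Reword the range sentence to say that rows with a rate above 12% lie outside the expected range and show how large a difference would be needed. It should add that within 2-12% power reaches about 80% only at comparator 12% vs apixaban 2%, and at most about 69% where apixaban is worse (2% vs 12%).

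The cost is a check of four table rows and one reworded sentence, with no change to sample size, conduct or planned analysis.
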